**Table JPBQ.6.2. Properties of Design for Progression-Free Survival**

Information Fraction	Cumulative Events	Cumulative Alpha Spent	Cumulative Beta Spent	Boundary Reject $H_0$ (1-sided p-value)
0.70	119	0.0082	0	<0.0082
1	170	0.0250	0.2	<0.0223

The actual alpha spent will be calculated based on the actual number of events observed at the time of analysis using software that implements the alpha-spending function noted above (for example, ADDPLAN 6.0 or SAS 9.2).

If the interim analysis crosses the boundary of significance at the pre-specified level, the study is considered positive. If statistical significance is not declared at the interim, the final PFS analysis will be conducted with approximately 170 PFS events. All remaining alpha will be spent at the final analysis on Cohort A. Once statistical significance is declared at either interim analysis or the final analysis, the study is considered positive.

### 6.7.1.3. Additional Analyses of the Primary Outcome

#### 6.7.1.3.1. Progression-Free Survival Curves and Hazard Ratio

The Kaplan-Meier (KM) method (Kaplan and Meier 1958) will be used to estimate the PFS curve for each treatment arm. Point estimates and confidence intervals for the first quartile, median, and third quartile for the PFS curve of each arm will be estimated. The PFS rates for each arm will be compared at 4 months intervals up to 24 months using a normal approximation for the difference between the rates.

A Cox proportional hazard model (Cox 1972) stratified by nature of disease and prior (neo)adjuvant endocrine therapy with treatment as a factor will be used to estimate the HR between the two treatment arms and the corresponding CI and Wald p-value (Agresti 2002).

#### 6.7.1.3.2. Restricted Mean Difference

The common method for describing benefit on the time scale is to calculate the difference in median event time between the two treatment arms. An alternative method for describing benefit on the time scale is to estimate the average difference between the KM curves. This corresponds to calculating the difference in the average time to event for the two treatment arms (Irwin 1949; Karrison 1997; Meier et al. 2004). Similar to the HR, this method uses all of the available information across the KM curves, but has the additional advantage of assessing benefit on the time scale.

To estimate an improvement in PFS with abemaciclib, we will follow the method of Irwin (1949) detailed in Karrison (1997) and Meier (2004) for estimating the ‘difference in average PFS’, which we will refer to more formally as the restricted mean difference in PFS.

The area under each KM curve will be calculated using numerical integration (trapezium rule) per Karrison and implemented in SAS using PROC LIFETEST. The difference between treatment arms and a CI for the difference will be formed.

Since the KM curve may be ill-determined beyond a certain range, or even undefined (if the longest observation is censored), for evaluation and comparison of means, the area under each KM curve will be calculated between time 0 and restriction time  $T$ , which is why this is referred to as a "restricted mean". Following the suggestion of Karrison, the restriction time  $T$  will be chosen as largest time point  $t$  such that the standard error ( $SE$ ) of the survival estimate at time  $t$  in each treatment group is no more than 0.075. For this purpose, we will use the simple, albeit conservative, formula proposed by Peto et al. (1977) for calculating the  $SE$  of  $S(t)$  as  $SE(S(t))=S(t) \cdot \frac{1 - S(t)}{n(t)}$ , where  $n(t)$  is the number of patients still at risk at time  $t$ .

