## 5.2. Determination of Sample Size

The study plan is to enroll approximately 450 patients in total, with 300 HR+, HER2- locoregionally recurrent or metastatic breast cancer patients who have not received prior endocrine therapy in Cohort A and 150 HR+, HER2- locoregionally recurrent or metastatic breast cancer patients in Cohort B. Assuming approximately 10% screening failure, the study will enter approximately 500 patients.

The approximate 300 patients qualified for Cohort A will be randomized in a 2:1 ratio to Arm A1 (abemaciclib plus NSAI; 200 patients) and Arm A2 (placebo plus NSAI; 100 patients). Patients will be randomized using the following stratification factors: nature of disease (visceral metastases vs. non-visceral metastases) and prior (neo)adjuvant endocrine therapy (prior therapy

with disease-free interval > 12 months from completion of treatment vs. prior therapy with disease-free interval ≤ 12 months from completion of treatment vs. no prior therapy).

A 2-look group-sequential design of the primary endpoint will be used to accommodate an event driven plan for the interim and primary PFS analyses (see protocol Section 12.2.6 for details). The primary PFS analysis will be performed after approximately 170 PFS events in Cohort A have occurred (ie, approximately 43% censoring rate). Assuming a hazard ratio of 0.626, this sample size yields at least 81.4% statistical power to detect superiority of the abemaciclib plus NSAI arm over the placebo plus NSAI arm with the use of a 1-sided log-rank test and a type I error of 0.025. If the true median PFS for the placebo plus NSAI arm is 14.4 months, then the hazard ratio of 0.626 amounts to an approximately 8.6-month (59.7%) improvement in median PFS for the abemaciclib plus NSAI arm under an additional assumption of exponential survival distribution.

Approximately 150 patients will be randomized in a 2:1 ratio to Arm B1 (abemaciclib plus fulvestrant; 100 patients) and Arm B2 (placebo plus fulvestrant; 50 patients). Patients will be randomized using the following stratification factors: nature of disease (visceral metastases vs. non-visceral metastases) and sensitivity to endocrine therapy (primary resistance vs. secondary resistance).

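### The trapezium rule named for the restricted mean PFS difference would, if applied point to point, overstate the gain by roughly 0.1 months; the exact step area costs nothing (minor)

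*SAP*

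**What the plan says.** SAP 6.7.1.3.2 (Restricted Mean Difference) offers the difference in average PFS time as an alternative to the difference in medians. On the computation it says: "The area under each KM curve will be calculated using numerical integration (trapezium rule". The same sentence refers to a cited methods paper and to SAS PROC LIFETEST.

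The areas run from 0 to a restriction time T. T is the largest time at which the standard error of the survival estimate "in each treatment group is no more than 0.075". For that standard error, the SAP says "we will use the simple, albeit conservative, formula" from a published source. In the text supplied, the formula reads S(t) × (1 − S(t))/n(t).

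The analysis stands in SAP 6.7.1.3, headed "Additional Analyses of the Primary Outcome". The confirmatory test is the one-sided stratified log-rank test of SAP 6.7.1.2. Under SAP 5.2, Cohort A "will be randomized in a 2:1 ratio to Arm A1 (abemaciclib plus NSAI; 200 patients) and Arm A2 (placebo plus NSAI; 100 patients").

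**The concern.** Between event times a Kaplan-Meier curve is flat. The area over the interval from t_i to t_{i+1} is therefore S(t_i) × (t_{i+1} − t_i), with nothing to approximate. The usual trapezium rule uses the average of S(t_i) and S(t_{i+1}) as the height, and so loses half of each drop multiplied by the interval length.

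The loss would matter little if it were equal in the two arms, but it is not. It grows with the size of the steps (a smaller arm) and with the total drop (faster progression). Both are greater in the placebo arm, so the error favours abemaciclib. At stake is a figure in months that describes average PFS benefit. No decision or alpha depends on it.

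**Working it through.** **Inputs from the documents.** 200 and 100 patients, 170 events, hazard ratio 0.626, control median 14.4 months, exponential PFS (SAP 5.2). One month is 365/12 days (SAP 6.1.2). Scans fall in the last 7 days of every second 28-day cycle through Cycle 18, then every third cycle (Protocol 10.1.1).

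**Assumptions.** Accrual duration is not stated separately; uniform accrual over 12 to 24 months was used across the runs. The runs reported in the first three table rows also assume no random dropout.

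**The plan's own figures.** SAP 6.7.1.3.2 gives no result to reproduce, so the design inputs were checked instead.
- Abemaciclib median: 14.4/0.626 = 23.0 months, a gain of 8.6 months, as stated.
- Single-look power: √(170 × 1/3 × 2/3) × |ln 0.626| = 2.879; 2.879 − 1.960 = 0.919, which gives 82.1%.
- With the two stated boundaries (0.0082 and 0.0223) power is 81.41%, against 81.4% stated.

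**Loss per arm.** Trapezium minus step area = −½ × Σ (t_{i+1} − t_i) × (S(t_i) − S(t_{i+1})).

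*Case 1: distinct event times, no censoring.* Each drop is 1/N, so the loss is about T/(2N). At T = 27.8 months:
- abemaciclib: 27.8/400 = 0.070
- placebo: 27.8/200 = 0.139
- the difference is inflated by 0.139 − 0.070 = 0.07 months

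Censoring makes the later steps larger, so the simulated losses are somewhat greater (first row of the table).

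*Case 2: all progressions dated on a common 8-week grid.* The interval is w = 56/(365/12) = 1.841 months, and the loss is (w/2) × (1 − S(T)). At T = 27 months:
- abemaciclib: S = 2^(−27/23.0) = 0.443, loss 0.9205 × 0.557 = 0.51
- placebo: S = 2^(−27/14.4) = 0.273, loss 0.9205 × 0.727 = 0.67
- the difference is inflated by 0.9205 × (0.443 − 0.273) = 0.16 months

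**Simulation at 170 events**, with T chosen using the standard error with its square root (months):

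| Event dating | Accrual | Step difference | Trapezium difference | Overstated by |
|---|---|---|---|---|
| Exact times | 20 | 3.547 | 3.636 | 0.089 (2.5%) |
| 8-week scans | 16 | 3.233 | 3.417 | 0.184 (5.7%) |
| 8-week scans | 20 | 3.408 | 3.598 | 0.190 (5.6%) |
| 8- then 12-week scans | 12 | 3.51 | 3.61 | 0.10 (2.8%) |
| 8- then 12-week scans | 18 | 3.73 | 3.84 | 0.11 (2.9%) |
| 8- then 12-week scans | 24 | 4.06 | 4.19 | 0.13 (3.2%) |

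In the first row the losses are 0.089 (abemaciclib) and 0.179 (placebo). In the third they are 0.532 and 0.722. Both arms lose area, and placebo loses more.

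**The standard error formula.** Without censoring, n(t) = N × S(t). At S = 0.5 and N = 100 (n = 50):
- as it appears in the text supplied: 0.5 × 0.5/50 = 0.005
- with a root: 0.5 × √(0.5/50) = 0.050, which equals the binomial value √(0.25/100)

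The number at risk needed to meet 0.075 at S = 0.4:
- without the root: 0.4 × 0.6/0.075 = 3.2
- with the root: 0.16 × 0.6/0.005625 = 17.1

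Only the version with the root fits a formula described as conservative and a limit of 0.075.

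**The case against.** **The software may already be exact.** The sentence that names the trapezium rule also names PROC LIFETEST. If that implementation sums the steps, or if trapezia are drawn through both corners of every step, the area is exact and nothing is overstated. The documents do not settle which applies. This objection stands as a limit on the effect: the size above applies only to point-to-point joining. It does not rescue the wording, because the usual reading of the named rule gives a different answer from the step area.

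**The effect is small and the analysis supportive.** Both are true. At 18-month accrual the excess is 0.11 months against a standard error of 1.30, less than a tenth of it (0.11/1.30 = 0.085).

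**A stronger reading that does not hold.** A reader might take the formula literally and infer that T runs into a tail with 2 or 3 placebo patients at risk. At 18-month accrual, the reader might then add the two effects: 4.45 months against 3.73, a 19% excess. The documents do not support this, for two reasons.
- The formula as supplied is the usual one with only the radical missing, and the surrounding words make sense only with it. Loss in PDF reading is the likelier explanation.
- Even taken literally, a later T defines a longer-horizon restricted mean, with a larger and noisier value. It does not bias the estimate. With exact event times, the simulated step estimate differed from the true value at its own T by −0.03 to 0.00 months. Of the 0.72-month gap (4.45 − 3.73), 0.57 (4.30 − 3.73) is this change of horizon and only 0.15 (4.45 − 4.30) is integration error.

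**Conclusion.** The point holds as a minor one. The trapezium rule is the wrong instrument for a step curve. Applied point to point at 170 events, it overstates the restricted mean PFS difference by roughly 0.1 months in favour of abemaciclib, with a range of about 0.07 to 0.2 months (2 to 6%). The upper end needs progressions dated on a common scan grid. The 7-day imaging window spreads the dates and moves the effect toward the lower end. The size rests on the SAP's exponential medians, the assumed accrual and, for the 8-week and exact-time runs, no dropout. It is zero if the program already sums the steps. The primary log-rank test, its boundaries and its alpha do not depend on it. The missing square root is a matter to check in the source PDF, not a finding.

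**What to change.** In SAP 6.7.1.3.2, replace the trapezium rule by the exact area under the step function: the sum of S(t_i) × (t_{i+1} − t_i) over event times up to T, with the last interval ending at T. Confirm that the PROC LIFETEST call or any supporting code does this.

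At the same time, check in the source PDF that the standard error in the rule for T is printed as S(t) × √((1 − S(t))/n(t)). If it is, nothing more is needed there.

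The cost is one line of SAP text and a program check. If the code had joined points, the reported difference would become slightly smaller; otherwise no result changes.

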## 6.7.2. Secondary Efficacy Analyses

### 6.7.2.1. Progression Free Survival of Cohort B

Progression-free survival in Cohort B is the key secondary endpoint for this study. The measurement, rules of censoring of PFS in cohort B are the same as those of PFS in Cohort A (refer to section 6.7.1). Only if statistical significance is declared at the Cohort A interim analysis, the interim analysis of Cohort B will be conducted based on the same data cutoff. If patients in Cohort A continue being followed for PFS until final analysis, the final analysis of Cohort B will be conducted at the same time of Cohort A final analysis. If Cohort A stops early at interim due to efficacy, the final analysis of Cohort B may be conducted after approximately 105 PFS events have been observed in Cohort B (that is, an approximately 30% censoring rate).

Similar to the analysis of PFS of cohort A, the KM method will be used to estimate the PFS curve for each treatment arm. A Cox proportional hazard model stratified by nature of disease and prior (neo)adjuvant endocrine therapy with treatment as a factor will be used to estimate the HR between the two treatment arms and the corresponding CI.

There will be no alpha spent for any test on this endpoint. Statistical tests, such as stratified log rank test and Wald test, will be purely descriptive.

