## 9.3. Method of Assignment to Treatment

Upon obtaining informed consent, site personnel should access the interactive web response system (IWRS). Patients who meet all criteria for enrollment will be randomly assigned to receive either abemaciclib plus NSAI/fulvestrant or placebo plus NSAI/fulvestrant. Assignment to treatment groups will be determined by a computer-generated random sequence using the IWRS. Sites will be prompted to enter the specific NSAI at time of randomization for patients in Cohort A.

Randomization will be stratified by the following in Cohort A: nature of disease (visceral metastases vs. non-visceral metastases), and prior (neo)adjuvant endocrine therapy (prior therapy with disease-free interval > 12 months from completion of treatment vs. prior therapy with disease-free interval ≤ 12 months from completion of treatment vs. no prior therapy).

Randomization will be stratified by the following in Cohort B: nature of disease (visceral metastases vs. non-visceral metastases) and sensitivity to endocrine therapy (primary resistance vs. secondary resistance).

The IWRS will be used to assign abemaciclib or placebo and distribute NSAI/fulvestrant supplied by Lilly (except distribution of NSAI in China). Site personnel will confirm that they have located the correct study medication packages by entering a confirmation number found on the packages into the IWRS.

The period between randomization to blinded study drug and the first dose (Cycle 1, Day 1) should not exceed 7 days.

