**Table JPBQ.12.2. Properties of Design for Progression-Free Survival**

Information Fraction	Cumulative Events	Cumulative Alpha Spent	Cumulative Beta Spent	Boundary Reject $H_0$ (1-sided p-value)
0.70	119	0.0082	0	<0.0082
1	170	0.0250	0.2	<0.0223

The actual alpha spent will be calculated based on the actual number of events observed at the time of analysis using software that implements the alpha-spending function noted above (eg, ADDPLAN 6.0 or SAS 9.2).

If the interim analysis crosses the boundary of significance at the pre-specified level, the study is considered positive. If statistical significance is not declared at the interim, the final PFS analysis will be conducted with approximately 170 PFS events. All remaining alpha will be spent at the final analysis on Cohort A. Once statistical significance is declared at either interim analysis or the final analysis, the study is considered positive.

The Cox proportional hazard model (Cox 1972) with treatment as a factor will be used to estimate the hazard ratio and corresponding 95% CI with Wald's test p-value after stratifying for the same randomization variables specified for the primary analysis.

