#### **12.2.7.1. Progression-Free Survival in Cohort B**

Progression-free survival in Cohort B is the key secondary endpoint for this study. The measurement, rules of censoring, and analysis methods of PFS in Cohort B are the same as those of PFS in Cohort A. Only if statistical significance is declared at the Cohort A interim analysis,

the interim analysis of Cohort B will be conducted based on the same data cutoff. No alpha specified for interim of Cohort B. If patients in Cohort A continue being followed for PFS until final analysis, the final analysis of Cohort B will be conducted at the same time of Cohort A final analysis. If Cohort A stops early at interim due to efficacy, the final analysis of Cohort B may be conducted after approximately 105 PFS events have been observed in Cohort B (that is, an approximately 30% censoring rate).

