### 6.4.2. Baseline Disease Characteristics

Disease characteristics will be summarized. Disease characteristics will include the following:

- Initial pathological diagnosis
- Study entry disease status (de novo metastatic disease vs. metastatic recurrent disease vs. locoregionally recurrent disease) for Cohort A
- Prior (neo)adjuvant endocrine therapy (aromatase inhibitor vs. other vs none)
- Prior (neo)adjuvant chemotherapy (yes or no) for Cohort B
- Prior metastatic endocrine therapy (aromatase inhibitor vs. antiestrogen vs. other vs. none) for Cohort B
- Disease-free interval (DFI)
- Treatment-free interval (TFI) for Cohort A
- Sensitivity to endocrine therapy (primary resistance vs. secondary resistance) for Cohort B
- Nature of disease (visceral metastases vs. non-visceral metastases )
- Measurable vs non-measurable disease
- Number of organs involved (1, 2, or 3+)
- Metastatic site
- Estrogen receptor status
- Progesterone receptor status.

Prior (neo)adjuvant endocrine therapy categories will be reported directly from the ‘Prior (neo)adjuvant endocrine therapy’ electronic case report form (eCRF). Prior metastatic endocrine therapy categories will be reported directly from the ‘Prior metastatic endocrine therapy’ eCRF.

Prior (neo)adjuvant chemotherapy will be reported based on data reported on the ‘Systemic Therapy: Prior for this Cancer’ eCRF.

Disease-free interval (DFI) is defined as the period of time between the completion of adjuvant endocrine therapy and disease recurrence for those patients who received adjuvant endocrine therapy. The categories (e.g. relapsed on or within 1 year vs. more than 1 year from completion of adjuvant endocrine therapy) will be reported directly from the ‘Breast Cancer Characteristics

A\_2' eCRF for Cohort A, and 'Breast Cancer Characteristics - B' eCRF for Cohort B, respectively.

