## 6.7. Efficacy Analyses

For cohort A, the stratification factors for the analysis of primary and secondary analyses are:

- nature of disease (visceral metastases vs non-visceral metastases)
- prior (neo)adjuvant endocrine therapy (prior therapy with disease-free interval  $>12$  months from completion of treatment vs. prior therapy with disease-free interval  $\leq 12$  months from completion of treatment vs. no prior therapy).

For cohort B, the stratification factors for the analysis of primary and secondary analyses are:

- nature of disease (visceral metastases versus non-visceral metastases)
- sensitivity to endocrine therapy (primary resistance versus secondary resistance).

The stratification factors are captured in the IWRS and on eCRFs. Unless otherwise specified, all stratified analyses will be based on the stratification factors per eCRF. A cross tabulation of the frequency of each level of each stratification factor per IWRS and eCRF will be produced.

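### SAP 6.7.2.1 stratifies the Cohort B PFS Cox model by a Cohort A factor, contradicting SAP 6.7 and the Cohort B randomisation

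*SAP*

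**What the plan says.** SAP 6.7.2.1 gives the model for the key secondary hazard ratio in Cohort B as "A Cox proportional hazard model stratified by nature of disease and prior (neo)adjuvant endocrine therapy with treatment as a factor". The same section says of the endpoint: "There will be no alpha spent for any test on this endpoint". It mentions a stratified log-rank test but does not name that test's strata.

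SAP 6.7 sets the stratification factors for the efficacy analyses separately by cohort. For Cohort B the second factor is "sensitivity to endocrine therapy (primary resistance versus secondary resistance"; prior (neo)adjuvant endocrine therapy is on the Cohort A list only. Protocol 9.3 reads "Randomization will be stratified by the following in Cohort B: nature of disease (visceral metastases vs. non-visceral metastases) and sensitivity to endocrine therapy", and SAP 5.3 agrees.

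The Cohort A model in SAP 6.7.1.3.1 is worded almost identically to the Cohort B model: "stratified by nature of disease and prior (neo)adjuvant endocrine therapy with treatment as a factor will be used to estimate the HR".

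**The concern.** A stratified Cox model would normally use the factors on which patients were randomised, and SAP 6.7 says that it will. SAP 6.7.2.1 names a different pair for Cohort B and gives no reason. A programmer who lets the specific section override the general one would drop sensitivity to endocrine therapy from the Cox model. The log-rank test, whose strata 6.7.2.1 leaves open, would fall back on 6.7. The test and the estimate for the same endpoint would then use different strata.

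The substituted factor also has no settled levels in Cohort B. SAP 6.7 defines it by disease-free interval, for Cohort A only. SAP 6.4.2 uses the same name for another grouping: "Prior (neo)adjuvant endocrine therapy (aromatase inhibitor vs. other vs none".

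Because the Cohort B tests are descriptive, the hazard ratio and confidence interval are the main reported result. SAP 6.13 allows a Cohort B interim analysis without a DMC that can inform talks with regulators on early stopping, unblinding and crossover. Two models that give different hazard ratios in the same data should not both be open once those data can be seen.

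**Working it through.** 1. The passages side by side. Nature of disease is common to all of them; only the second Cohort B factor differs.

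| Place | Second factor for Cohort B |
|---|---|
| Randomisation: Protocol Synopsis, 8.1, 9.3, 12.1; SAP 5.1, 5.2, 5.3 | sensitivity to endocrine therapy |
| Analysis factors: SAP 6.7 | sensitivity to endocrine therapy |
| Log-rank test, both cohorts: Protocol Synopsis | the stratification variables |
| Cox model: SAP 6.7.2.1 | prior (neo)adjuvant endocrine therapy |

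The exception clause in SAP 6.7 concerns whether eCRF or IWRS values are used, not which factors apply, so it does not license the difference. No other text explains it.

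2. Number of strata. The 6.7 factors give 2 x 2 = 4 strata, or 105/4 = 26.25 events each on average. The 6.7.2.1 wording with Cohort A's three levels gives 2 x 3 = 6 strata, or 105/6 = 17.5 events each.

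3. The plan's own benchmark (Protocol 12.1, SAP 5.2): roughly an 80% chance of an observed HR below 0.824 when the true HR is 0.703. With 2:1 allocation and d events, SE(log HR) = sqrt(9/(2d)). At d = 105 this is sqrt(9/210) = 0.207. Then ln(0.824/0.703) = 0.159, 0.159/0.207 = 0.767, and the probability is 77.9%. It reaches 80% at about 126 events. The documents tie the benchmark to no event count, so 77.9% is compatible with roughly 80%.

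4. Effect of the strata, by simulation. From the documents: 150 patients, 2:1, 105 events, true HR 0.703. The documents give no prevalences or prognostic effects, so these were assumed:
   - primary resistance in 20%, 30% or 40%, with prognostic HR 1.0, 1.5, 2.0 or 3.0;
   - prior-therapy HR 1.0 or 1.5 for the group with disease-free interval of 12 months or less, and levels of 30/40/30%;
   - prior therapy either independent of resistance, or dependent (half of primary-resistant patients placed in that group);
   - 60% visceral disease with HR 1.4, control median 9 months, exponential times, 18-month uniform accrual.

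   This gives 4 x 3 x 2 x 2 = 48 scenarios of 3,000 trials each. At 30% prevalence, independent, prior-therapy HR 1.0:

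| Resistance HR | HR, 6.7 strata | HR, 6.7.2.1 strata | SE, 6.7 vs 6.7.2.1 | Opposite sides of 0.824 |
|---|---|---|---|---|
| 1.0 | 0.702 | 0.702 | 0.208 vs 0.213 | 6.0% |
| 1.5 | 0.702 | 0.707 | 0.208 vs 0.213 | 7.3% |
| 2.0 | 0.697 | 0.711 | 0.209 vs 0.213 | 9.1% |
| 3.0 | 0.701 | 0.728 | 0.210 vs 0.214 | 10.9% |

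   At 30%, dependent, prior-therapy HR 1.5, the pairs are 0.704 vs 0.703, 0.701 vs 0.709 and 0.704 vs 0.726 for resistance HR 1.5, 2.0 and 3.0.

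   Change in mean HR over the whole grid (6.7.2.1 minus 6.7), by resistance HR:
   - 1.0: -0.008 to +0.001
   - 1.5: -0.004 to +0.005
   - 2.0: +0.004 to +0.015
   - 3.0: +0.014 to +0.035

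   The mean SE is 1.3-2.7% larger with the 6.7.2.1 strata. The median absolute difference within one trial is 0.026-0.057, and the two HRs straddle 0.824 in 6-15% of trials.

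5. A separate simulation under other assumptions (visceral HR 1.5, 30% resistance, prior therapy unrelated to outcome, 1,500 trials per scenario) gave 0.70 throughout with the randomisation strata. With the 6.7.2.1 strata it gave 0.70, 0.71, 0.72 and 0.74 for resistance HR 1.0, 1.5, 2.0 and 3.0.

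6. Scale against sampling error. With HR 0.70 and SE 0.21, the 95% interval is 0.70 x exp(±1.96 x 0.21), about 0.46 to 1.06. The largest shift in the table is ln(0.728/0.701)/0.21 = 0.18 standard errors, towards the null.

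**The case against.** The strongest textual point is that the protocol can be read as supporting 6.7.2.1. Protocol 12.2.6 fits the Cox model "after stratifying for the same randomization variables specified for the primary analysis", and for Cohort A those variables include prior (neo)adjuvant endocrine therapy. Protocol 12.2.7.1 then says that "analysis methods of PFS in Cohort B are the same as those of PFS in Cohort A". Taken literally, the two carry Cohort A's factors into Cohort B. The more natural reading is that the method carries over with each cohort's own randomisation factors, but that is an inference, so these two sections are best treated as ambiguous. The contradiction does not need them: SAP 6.7, SAP 5.3 and Protocol 9.3 are explicit.

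On size, the straddling rate overstates the harm. It is 6.0% even when resistance has no prognostic effect, because any two sets of strata give somewhat different estimates. In the tabulated case only 10.9 - 6.0 = 4.9 percentage points are added as the resistance HR rises to 3.0. The within-trial difference is likewise never zero. The value 0.824 is a sample-size benchmark, not a decision rule. The mean shift is small against the confidence interval, every prognostic input is assumed, and the 105-event count applies only if Cohort A stops early. All of this stands.

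It is also fair that the sentence looks copied from the Cohort A section, so the intent can be guessed, and that SAP 6.11 already plans Cohort B subgroup hazard ratios by the stratification factors. A guessed intent is not a specification, though, and subgroup estimates do not replace the overall one. The ambiguity over the factor's levels is secondary: the only stratification definition is Cohort A's, and 6.4.2 is a baseline table.

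**Conclusion.** The concern holds. SAP 6.7.2.1 is wrong as written: it conflicts with SAP 6.7 and with the Cohort B randomisation, and nothing in either document justifies a different set of factors. This conclusion rests on the text alone.

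The consequence is confined to the reported Cohort B hazard ratio and confidence interval and their consistency with the log-rank test. The Cohort A test, the sample size and the alpha are unaffected. Under the assumed inputs the average distortion ranges from negligible to modest, depending on how prognostic primary resistance is. The stronger reason to act is that two different estimates of the key secondary effect can currently be defended from the same SAP. It should be fixed, but it does not threaten the trial's main conclusion.

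**What to change.** In SAP 6.7.2.1, replace prior (neo)adjuvant endocrine therapy with sensitivity to endocrine therapy (primary or secondary resistance). State that the Cohort B Cox model and log-rank test both use the two Cohort B randomisation factors listed in SAP 6.7. Keep the statement that no alpha is spent and the tests are descriptive.

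Make the change before sponsor unblinding of Cohort B. Protocol 12.2.1 allows clarifications of this kind in the SAP up to sponsor unblinding of the aggregate database. It needs no new data, because SAP 6.7 says the stratification factors are captured in both the IWRS and the eCRFs. No event count, power or alpha figure changes.
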